7.0 Statistical Considerations

Because of limited funding from NIH, the number of patients that are planned to be enrolled into this protocol will be small and potentially lacking of the statistical power. The primary purpose of this study is a feasibility study to test whether a combined CBCT and ultrasound image guidance is clinically feasible. Our analysis is primarily descriptive and does not require any advanced statistics to analyze the endpoints. As a measure of protocol success we expect that:

- 1) Over 80% of patients have ultrasound images which are clinically adequate for treatment set-up in the judgment of the treating physician.
- 2) Over 80% of patients are able to undergo ultrasound based tumor tracking during treatment.
- 3) The quality of treatment plans for more than 80% of patients will not be affected.
- 4) No adverse events related to the ultrasound probe are noted during treatment.

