3.0 Patient/Sample Selection

We will recruit a total of 30 patients, 30 with prostate cancer that will undergo external beam treatment at the Department of Radiation Oncology.

All patients undergoing radiation treatment for prostate cancer, with EBRT or SBRT are eligible.

A completed patient eligibility checklist is required following the approved standard operating procedure of the enrolling institution.

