5.0 Research Plan

5.1 Investigate whether the ultrasound imaging can enhance soft tissue tumor localization.

(a) Following the standard clinical procedure, daily KV-CBCT image for each patient will be acquired and used to guide for patient setup prior to treatment delivery. Because of limited soft tissue contrast in KV-CBCT to observe the soft tissue organ, such as the prostate, the added ultrasound image may enhance soft tissue localization prior to treatment for these patients.

The ultrasound device will be calibrated to the treatment iso-center via an external camera system and infrared markers on the ultrasound (US) probe. A commercially available passive arm will be acquired and attached to the ultrasound probe. Following our current clinical protocol, the patient treatment position will be determined solely based the daily KV-CBCT. After KV-CBCT guidance, a pre-treatment US image will be acquired for the study but not used for patient positioning. The success of this specific aim is defined as that the tumors can be visualized in the ultrasound images in at least 80% of patients enrolled.

(b) Investigate whether the presence of a passive arm will interfere with radiation delivery during each treatment.

In order to monitor tumor or organ motion during radiation, the US probe will be placed using a passive arm, as shown in the figure below. This passive arm will be attached to the treatment couch and also in contact with the patient during the radiation. Although the passive arm is commercially available, we plan to test whether the presence of the US probe will interfere radiation delivery during each treatment. Specifically, we will test: (a) whether the passive arm reduces the clearance between the patient and the gantry of the linear accelerator; (b) whether the passive arm can hold a consistent contact pressure with the patient under normal breathing motion; (c) whether the passive arm can be automatically released if a patient makes a large movement. The success of this specific aim is defined as that at least 80% of patients are able have the ultrasound probe attached during the entire treatment course.

Figure 1.

(c) Investigate whether the presence of the ultrasound probe will interfere with the choice of radiation beams and degrade plan quality

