6.0 Study Parameters

The study parameters collected are the US images acquired prior to each treatment and during radiation delivery. Pre-treatment KV-CBCT images will also be collected for dosimetric analysis. Specifically, the tumor location detected from combined US/KV-CBCT images will be compared with using KV-CBCT alone. Using the KV-CBCT the gold standard, 3D radiation dose distributions will be re-calculated according to the tumor localizations using KV-CBCT alone and using combined US/KV-CBCT. For SBRT prostate cancer, we will compare the following dosimetric endpoints, extracted from dose volume histograms.

Organ Name	Endpoint 1	Constraints
PTV_HD*	V5000 cGy	> 50%
PTV_LD*	V3625 cGy	> 95%
PROSTATE	V3625 cGy	> 95%
BLADDER	D0.03 cc	< 5250 cGy
RECTUM_ANT	D0.03 cc	<5000 cGy
RECTUM_LAT	D3cc	< 4000 cGy
RECTUM_POST	V0.03 cc	< 2250 cGy
URETHRA	V0.03cc	< 5000 cGy
URETHRA	D1cc	< 4500 cGy

PTV_HD = planning target volume in high dose prescription dose of 5000 cGy

PTV_LD = planning target volume in low prescription dose of 3625 c Gy.

For patients treated with conventional multiple fractionation, we will compared the following dosimetric endpoints, extracted from dose volume histograms.

Organ Name	Endpoint 1	Constraints	Planned	comments
CTV_7800	V7800 cGy	> 99%		
PTV_7800	V7800 cGy	> 95%		
BLADDER	V7000 cGy	< 10%		
BLADDER	V6000 cGy	< 20%		
RECTUM	V7000 cGy	< 10%		
RECTUM	D10cc	< 7000 cGy		
RECTUM	V5000 cGy	< 30%		Without pelvic nodes
RECTUM	V5000 cGy	< 50%		With pelvic nodes
FEMORAL HEAD_L	V5000 cGy	< 5%		
FEMORAL HEAD_R	V5000 cGy	< 5%		
PENILE BULB	Dmean	< 5250 cGy		

For patients with prostatectomy receiving post-operative radiotherapy with conventional multiple fractionation, we will compared the following dosimetric endpoints, extracted from dose volume histograms.

Organ Name	Endpoint 1	Constraints	Planned	comments
CTV_7000	V7000 cGy	> 99%		
PTV_7000	V7000 cGy	> 95%		
BLADDER	V6500 cGy	< 40%		
BLADDER	V4000 cGy	< 60%		
RECTUM	V6300 cGy	< 10 %		
RECTUM	D10 cc	<6300 cGy		

RECTUM	V4500 cGy	< 30 %		Without Pelvic nodes
RECTUM	V4500 cGy	< 50%		With pelvic nodes
FEMORAL HEAD_L	V5000 cGy	< 5%		
FEMORAL HEAD_R	V5000 cGy	< 5%		
PENILE BULB	Dmean cGy	< 5250 cGy		

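### Criterion 1 is a subjective ultrasound judgment made after KV-CBCT guidance with no masking specified, so it is at risk of being informed by KV-CBCT, more plausibly towards success

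*Combined protocol and SAP*

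**What the plan says.** Section 7.0 lists four measures of protocol success. The first is that "Over 80% of patients have ultrasound images which are clinically adequate for treatment set-up in the judgment of the treating physician". Section 5.1(a) sets a related but different target for the same aim, that "the tumors can be visualized in the ultrasound images in at least 80% of patients enrolled", and names no assessor.

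Section 5.1(a) also fixes the order of events. The ultrasound is calibrated to the treatment isocentre, and "the patient treatment position will be determined solely based the daily KV-CBCT". Then: "After KV-CBCT guidance, a pre-treatment US image will be acquired for the study but not used for patient positioning".

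Section 6.0 plans a comparison in which "the tumor location detected from combined US/KV-CBCT images will be compared with using KV-CBCT alone". It continues: "Using the KV-CBCT the gold standard, 3D radiation dose distributions will be re-calculated" for each of the two localizations.

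On size and analysis, section 3.0 states "We will recruit a total of 30 patients, 30 with prostate cancer", and section 7.0 states "Our analysis is primarily descriptive and does not require any advanced statistics to analyze the endpoints".

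Sections 5.1, 6.0 and 7.0 do not say when or where the ultrasound is read, whether the KV-CBCT is in view, or what standard defines adequacy. They provide no masked or independent read, and no rule that turns many daily images into one result per patient.

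**The concern.** Section 1.0 gives the reason for adding ultrasound: KV-CBCT separates soft tissue poorly. Objective (a) in section 2.0 asks whether ultrasound improves soft tissue localization. Criterion 1 and the aim (a) target should therefore show what can be recognised in the ultrasound images.

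A reader who knows the KV-CBCT position, and knows that the ultrasound shares the isocentre, has an expectation of where the target should lie. That reader may accept an image in which the target could not have been found unaided. A target that is seen and a target that is inferred then count the same. Because the ultrasound never determines position, a lenient call has no set-up consequence that would expose it.

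At stake is a declared measure of protocol success. Section 8.8 says that the data will help design a later, adequately powered protocol, so an inflated adequacy rate would carry forward.

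**Working it through.** **Nothing to reproduce.** The plan gives no power, error rate or sample-size derivation. The figures below are illustrations with assumed rates.

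**Inputs from the documents**
- N = 30 (section 3.0). Patients whose probe is removed for plan-quality reasons stay in 5.1(a) (section 5.1(c)), so 30 is the denominator.
- Criterion 1: over 80% (section 7.0). 0.80 × 30 = 24, so the smallest passing count is 25.
- Aim (a): at least 80% (section 5.1(a)), so 24 passes.

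**Assumed inputs, not in the documents**
- p: the true share of patients with adequate images.
- f: the share of truly inadequate sets called adequate.
- s: the share of truly adequate sets called inadequate.
- Patients are independent and share the same misread rates.

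**Step 1: how many changed reads matter.** Take p = 0.70, so 0.70 × 30 = 21 adequate and 9 inadequate.
- Three of nine called adequate: 24/30 = 80.0%. This fails criterion 1 but meets the aim (a) threshold.
- Four of nine (44%) called adequate: 25/30 = 83.3%. This passes both thresholds.

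**Step 2: chance of a pass with upward error only.** The observed rate is q = p + (1 − p)f, and P(pass) = Σ C(30,k) q^k (1 − q)^(30−k) for k = 25 to 30.

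For p = 0.70 and f = 0.25: q = 0.70 + 0.30 × 0.25 = 0.775. P(pass) rises from 0.077 at f = 0 to 0.303.

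| True p | f = 0 | f = 0.10 | f = 0.25 | f = 0.50 |
|---|---|---|---|---|
| 0.60 | 0.006 | 0.018 | 0.077 | 0.428 |
| 0.70 | 0.077 | 0.141 | 0.303 | 0.711 |
| 0.75 | 0.203 | 0.303 | 0.497 | 0.836 |

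Under the 24/30 rule, the same change at p = 0.70 (f from 0 to 0.25) takes the chance from 0.16 to 0.47.

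**Step 3: error in the other direction.** With f = 0, q = p(1 − s). For p = 0.70 and s = 0.10, q = 0.63 and P(≥25/30) falls from 0.077 to 0.014.

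**Step 4: when the two errors cancel.** The expected rate is unchanged when p × s = (1 − p) × f. At p = 0.70 and f = 0.25, s = 0.075/0.70 = 0.107. Strict reading of about one adequate set in nine would offset lenient reading of a quarter of the inadequate ones. The net sign is therefore not fixed by arithmetic. It depends on reading conditions that the plan leaves open.

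**The case against.** **Combined imaging is the intended use.** Section 2.0 sets out to combine the two modalities, and section 1.0 says that ultrasound alone has too small a field of view. Reading ultrasound beside KV-CBCT is consistent with that purpose. This stands as a reason to keep the combined localization. It does not rescue criterion 1, because both that criterion and the aim (a) target are worded about the ultrasound images themselves.

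**Section 6.0 already tests added value.** It compares recorded localizations and recalculates dose, which is a partial check. But the combined localization includes the KV-CBCT, which is also the declared gold standard. The comparison cannot show whether the target was recognisable on ultrasound before the KV-CBCT was consulted.

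**The cue may be weak.** By the protocol's own account KV-CBCT shows the prostate poorly, so it does not hand the reader a precise answer. This stands, and it limits how large the effect may be.

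**The study is small and descriptive.** True, but criterion 1 is still a stated measure of success.

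**Stronger readings that the documents do not support.** A reader might infer that the KV-CBCT is on display during the read, or that the assessor is the physician who approved that day's set-up. The documents say neither. A reader might also infer that errors can run only upward; step 3 shows the effect of the opposite error. Nor are three changed reads enough for criterion 1 from 21/30, since exactly 80% does not exceed 80%. Positioning on KV-CBCT follows the current clinical protocol and is not the flaw.

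**Conclusion.** The concern holds as a risk of bias. Criterion 1 is a subjective judgment on images acquired after KV-CBCT guidance, untested by any set-up decision, and no masking or adequacy standard is specified. Upward bias is the more plausible direction, because prior knowledge of position helps recognition and leniency has no set-up consequence. That direction is an inference.

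The size is unknown. Four changed reads would turn 21/30 into a pass on criterion 1, and a 25% lenient-read rate would roughly quadruple the chance of passing at a true rate of 70% (0.303/0.077 ≈ 3.9). Both results rest on assumed rates. That actual cueing occurs, or that the reported rate will be inflated, is not established. The gap deserves correction because the result decides a stated success measure and the remedy is cheap.

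**What to change.** In sections 5.1(a) and 7.0, state that:

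1. Visualization and adequacy are scored by the same treating physician from the stored ultrasound images, with that day's KV-CBCT and its registration hidden.
2. The read covers a prespecified set of fractions per patient, presented in shuffled order across patients and fractions.
3. A written rule converts the fraction-level scores into one result per patient.
4. The scores are locked before the KV-CBCT is shown, and criterion 1 uses these locked scores.
5. The KV-CBCT is then shown for the combined US/KV-CBCT localization in section 6.0, which is otherwise unchanged.

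No extra reader, patient or imaging is needed, and patient positioning is not altered. The cost is protocol wording, some offline reading time and possibly a lower adequacy rate. Masking will be incomplete: the same physician may recall the case, and the patient was already aligned when the image was acquired. The report should say so.

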The presence of the US probe and the passive arm may block the access of some radiation beams. The specific aim of this study to investigate whether altering the radiation beam directions will affect the treatment plan quality. Our preliminary planning data[1] showed that it is necessary to choose different radiation beam angles, but the impact on treatment plan quality is not clinically significant for most patients. Patients for whom treatment plan quality is in the opinion of the treating physician adversely impacted by alteration of beam angles required by presence of the US probe will be treated with the non-altered plan, and thus be included in step 5.1(a), but excluded from 5.1(b&c), as US probe will be removed prior to treatment in these cases to allow for treatment with the best possible plan. We expect this to be rare. The success of this specific aim is defined as that the quality of the plans for 80% of patients will not be affected in the presence of the

ultrasound probe, defined as no more than a 2% decrease in tumor coverage, and also no more than a 2% increase in the dose to the most critical normal tissue for that tumor location (Prostate: dose to hottest 10 cc of rectum.)

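### Sections 5.1 and 7.0 set two different success rules for the same aims, and the protocol does not say which one governs

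*Combined protocol and SAP*

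**What the plan says.** Section 3.0 fixes the size of the study: "We will recruit a total of 30 patients, 30 with prostate cancer". Section 5.1 then defines success aim by aim:

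- Aim (a): "the tumors can be visualized in the ultrasound images in at least 80% of patients enrolled".
- Aim (b): "at least 80% of patients are able have the ultrasound probe attached during the entire treatment course".
- Aim (c): "the quality of the plans for 80% of patients will not be affected", where unaffected means a loss of tumor coverage of at most 2% and a rise in dose to the critical normal tissue of at most 2%.

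The text under 5.1(c) adds that patients whose plan the physician considers harmed by the altered beam angles keep their original plan. They count for (a) but are left out of (b) and (c).

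Section 7.0 gives a second list as its yardstick for protocol success:

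- Item 1: "Over 80% of patients have ultrasound images which are clinically adequate for treatment set-up in the judgment of the treating physician".
- Item 2: "Over 80% of patients are able to undergo ultrasound based tumor tracking during treatment".
- Item 3: plan quality unaffected in more than 80% of patients, without repeating the 2% limits.
- Item 4: no probe-related adverse events.

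Neither section refers to the other, and nothing states which list takes precedence.

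**The concern.** The study has one arm and no hypothesis test, so these benchmarks are the only pre-stated basis for calling it a success. If two sections state them differently, a team that follows the plan faithfully can report a given aim as both met and not met. The data are also meant to support the design of a later, adequately powered protocol (Section 8.8), so readers will want to know what a reported success refers to: a visible tumor or a usable image, a probe that stayed on or a target that could be followed.

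**Working it through.** **Step 1. Set the criteria side by side.**

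| | Section 5.1 | Section 7.0 | Same endpoint? | Same cut-off? |
|---|---|---|---|---|
| (a) / item 1 | tumor visualized; at least 80% of those enrolled | image adequate for set-up, physician's judgment; over 80% | no | no |
| (b) / item 2 | probe attached for the whole course; at least 80% | able to be tracked by ultrasound; over 80% | no | no |
| (c) / item 3 | plan unaffected under the 2%/2% limits; 80%, no inequality given | plan unaffected, limits not repeated; more than 80% | nominally yes | unclear |
| item 4 | none | no probe-related adverse events | no counterpart | no counterpart |

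**Step 2. Can the endpoints disagree?** For (a), a tumor may be visible on an image that the physician judges inadequate for set-up. The reverse is also possible: Section 3.1.1 admits patients after prostatectomy, who may have no tumor to see although the image is usable. For (b), a probe may stay attached without giving an image on which the target can be followed. Section 8.2 commits only to counting probes attached and removed, which does not measure tracking. Section 6.0 does collect ultrasound images during delivery, so a tracking endpoint can be assessed. The documents give no data from which to put a size on these disagreements, and they do not depend on the number of patients.

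**Step 3. Turn the cut-offs into whole patients.** With n patients in the denominator, at least 80% needs the smallest integer not below 0.8n, and over 80% needs the smallest integer above 0.8n.

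| n | at least 80% | over 80% | differ? |
|---|---|---|---|
| 30 | 24 | 25 | yes |
| 29 | 24 | 24 | no |
| 28 | 23 | 23 | no |
| 27 | 22 | 22 | no |
| 26 | 21 | 21 | no |
| 25 | 20 | 21 | yes |
| 24 | 20 | 20 | no |

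The gap exists only when n is a multiple of 5. Aim (a) is stated among patients enrolled, so at full accrual n = 30 and the gap applies. For (b) and (c), n is 30 less the patients left out under 5.1(c), a number not known in advance.

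**Step 4. How often would the cut-off alone split the verdict on aim (a)?** The plan gives no figure to reproduce. Take X as binomial with n = 30 and true rate p, and suppose for this step that the same patients count as successes in both sections. The sections then disagree only at X = 24:

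P(X = 24) = C(30,24) × p^24 × (1 − p)^6, with C(30,24) = 593,775.

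At p = 0.80 this is 593,775 × 0.80^24 × 0.20^6 = 0.179. The values of p are assumptions.

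| true rate p | meets 5.1 (24 or more) | meets 7.0 (25 or more) | exactly 24: sections disagree |
|---|---|---|---|
| 75% | 34.8% | 20.3% | 14.5% |
| 80% | 60.7% | 42.8% | 17.9% |
| 85% | 84.7% | 71.1% | 13.7% |
| 90% | 97.4% | 92.7% | 4.7% |
| 95% | 99.9% | 99.7% | 0.3% |

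The last column is computed directly and may differ from the difference of the other two in the last digit.

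**Step 5. Precision.** The exact (Clopper-Pearson) 95% limits for x of n are the 2.5% quantile of Beta(x, n − x + 1) and the 97.5% quantile of Beta(x + 1, n − x). For 24/30 these are Beta(24, 7) and Beta(25, 6), giving 61.4% to 92.3%. For 25/30 the limits are 65.3% to 94.4%.

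**The case against.** The plan calls itself a small feasibility study with a mainly descriptive analysis, admits that power may be lacking, and attaches no test or treatment consequence to the benchmarks. Section 5.1 speaks of success of an aim and Section 7.0 of success of the protocol, so the second list could be a stricter upper tier. If the true rates are well above 80%, as the plan's wording suggests it expects, the one-patient gap rarely matters: 4.7% at a true rate of 90% and 0.3% at 95%.

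Much of this stands, and it limits what can be claimed. Three stronger readings are tempting, and the documents support none of them:

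- A reader might infer that 24 against 25 applies to all three aims. It applies with certainty only to (a) at full accrual. The wording of 5.1(c) has no inequality, and the denominators for (b) and (c) may fall below 30.
- A reader might infer that a go/no-go decision hangs on the result, or that the verdict will be picked once the data are in. No such decision is described. The text leaves the choice open but shows no intent to use it.
- A reader might infer that the plan treats 24 or 25 of 30 as proof of a true rate above 80%. It makes no such claim, so the width of the interval is a matter of reporting and not an error.

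What does not stand is the defence that a descriptive study can leave success defined two ways. The two-tier reading is possible but is nowhere stated, and it would not explain why the endpoints, and not only the thresholds, change between sections.

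**Conclusion.** The criteria are inconsistent as written and need to be reconciled before analysis. The larger part of the problem is that aims (a) and (b) carry different endpoints in the two sections. This can produce opposite verdicts at any sample size, and its size cannot be estimated from the documents.

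The smaller part is the cut-off. For aim (a) with all 30 patients enrolled, a result of 24 meets 5.1 and misses 7.0. This is most likely at a true rate of 80% (17.9%) and becomes less likely as the true rate rises. The figure assumes independent patients, full accrual and the same count of successes under both endpoints. For (b) and (c) the cut-off gap is conditional on the final denominator, and for (c) also on how the unqualified 80% is read.

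In addition, a single probe-related adverse event fails 7.0 while every aim in 5.1 can still be met.

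**What to change.** Before analysis, amend 5.1 and 7.0 so that each criterion has one endpoint, one denominator and one inequality, in identical words.

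- **(a)** Target visualized and image judged adequate for set-up, among all enrolled.
- **(b)** Probe in place for the whole course, with the target visible on the during-delivery ultrasound images that Section 6.0 already collects. Add a per-patient rule for combining fractions.
- **(c)** The 2%/2% rule of 5.1, repeated or cited in 7.0.
- **Cut-off.** At least 80% throughout, or over 80% throughout. Express it as a proportion so that it still works if accrual falls short of 30.
- **Denominator for (b) and (c).** State whether patients left out under 5.1(c) are removed or counted as not meeting the criterion. For illustration, if 5 of 30 were left out and 20 of the other 25 met the criterion, the result would be 20/25 = 80.0% on one rule and 20/30 = 66.7% on the other.
- **Item 4.** List it in both sections, or say that 7.0 adds it for overall protocol success.
- **Reporting.** Give each proportion with its exact 95% confidence interval as a description of precision.

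The cost is a wording amendment and three intervals, with no added patients, visits or imaging; the during-delivery images must be scored for target visibility. The downside is that the combined definitions of (a) and (b) are harder to meet than the present 5.1 wording.
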